8.4. Vital Signs

Values at each scheduled visit, change, and percent change from baseline for vital signs, including weight, height, SBP, DBP, pulse, respiration rate, and body temperature will be summarized descriptively.

Criteria for clinically notable vital sign abnormalities are defined in [Table 7](#). The abnormal values for participants exhibiting clinically notable vital sign abnormalities will be listed along with their assigned treatment group. Alert vital signs are defined as an absolute value outside the defined range and percentage change greater than 25%. The abnormal values for participants exhibiting alert vital sign abnormalities will be listed.

Table 7: Criteria for Clinically Notable Vital Sign Abnormalities

Parameter	High Threshold	Low Threshold
Systolic blood pressure	> 155 mmHg	< 85 mmHg
Diastolic blood pressure	> 100 mmHg	< 40 mmHg
Pulse	> 100 bpm	< 45 bpm
Temperature	> 38°C	< 35.5°C
Respiratory rate	> 24/min	< 8/min

8.5. Electrocardiograms

Twelve-lead ECGs will be obtained for each participant during the study. Electrocardiogram abnormalities, both at baseline and postbaseline visits, will be tabulated by treatment group for the initial portion and crossover portion separately. Incidences of abnormalities will be listed with study visit, assigned treatment group, and a description of the abnormality.

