#### 9.4.2.4. Electrocardiograms

Descriptive statistics and mean change from baseline will be determined for each ECG parameter at each assessment time. Electrocardiogram results will be reviewed for clinically notable abnormalities according to predefined criteria ([Table 13](#)). Subjects exhibiting clinically notable ECG abnormalities will be listed.

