**Table 13: Criteria for Clinically Notable Electrocardiogram Abnormalities**

Parameter	High Threshold	Low Threshold
QTcF	> 460 msec	< 295 msec
PR	> 220 msec	< 75 msec
QRS	> 120 msec	< 50 msec
QT	> 500 msec	< 300 msec
RR	> 1330 msec	< 600 msec

QTcF = Fridericia correction.

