10.1. Changes to Protocol-Defined Analyses

Not applicable.

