2.10 ECG	
2.10.1	12-Lead ECG Values
2.10.2	Abnormal 12-Lead ECG Values
2.10.3	Alert 12-Lead ECG Values

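### SAP 8.5 omits the Protocol's by-visit ECG summaries and Table 13 limits, and SAP 10.1 does not record the change; individual ECG values are still listed

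*SAP*

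**What the plan says.** Protocol 9.4.2.4 makes three commitments for ECGs:

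- Summary of the measurements: "Descriptive statistics and mean change from baseline will be determined for each ECG parameter at each assessment time".
- Review against limits: "Electrocardiogram results will be reviewed for clinically notable abnormalities according to predefined criteria". The limits are in Table 13, "Criteria for Clinically Notable Electrocardiogram Abnormalities", with a high and a low threshold for QTcF, PR, QRS, QT and RR.
- Use of that review: "Subjects exhibiting clinically notable ECG abnormalities will be listed".

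Protocol 9.4 leaves the full description of the analyses to the SAP.

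SAP 8.5 is two sentences of analysis. The first is "Electrocardiogram abnormalities, both at baseline and postbaseline visits, will be tabulated by treatment group", split by initial and crossover portion. The second plans a listing of abnormalities with visit, assigned group and a description. SAP Appendix A holds Tables 3.5.1.1 and 3.5.1.2, whose shared title covers only treatment-emergent abnormalities of clinical significance. It also holds Listings 2.10.1 (ECG values), 2.10.2 (abnormal values) and 2.10.3, "Alert 12-Lead ECG Values". SAP 10.1, the place for departures from the Protocol's analyses, reads "Not applicable".

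**The concern.** A safety analysis that the Protocol defines is missing from the document meant to carry it out, and the section for such changes says there are none. A programmer who follows the SAP as written will produce no mean, median or change from baseline for any ECG parameter.

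A table of abnormalities judged clinically significant and a table of parameter change answer different questions. The first counts individual events that depend on a reader's judgement; Protocol 7.5.4 gives that judgement to the site investigator. The second can show a modest shift across a whole regimen in which no single tracing looks remarkable. The SAP keeps only the first. Changes in safety assessments are part of a secondary endpoint (SAP 2.3.2), so this is a gap in a planned analysis and not only in presentation.

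**Working it through.** No sample size, power or error rate is involved, so the check sets the two documents side by side.

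| Element | Protocol | SAP |
|---|---|---|
| Statistics and mean change per parameter, by visit | Planned (9.4.2.4) | None in 8.5; 0 tables and 0 figures in Appendix A |
| Numerical limits | Table 13, 5 parameters: QTcF > 460 or < 295 msec; PR > 220 or < 75; QRS > 120 or < 50; QT > 500 or < 300; RR > 1330 or < 600 | 0 of 5 parameters |
| Listing of notable values | Planned, by the Table 13 limits | Listings 2.10.2 and 2.10.3, with no ECG criterion given |
| Individual values | Not separately specified in 9.4.2.4 | Listing 2.10.1 |
| Table of abnormalities | Not specified in 9.4.2.4 | 8.5 and 2 tables (3.5.1.1, 3.5.1.2) |
| Record of the change | Not applicable to the Protocol | 0 of 4 places (10.1, 10.2.1, 10.2.2, 10.2.3) |

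Three cases show what would and would not be seen under the SAP.

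1. **A group shift.** Suppose QTcF rises in one regimen but every value stays at or below 460 msec. Nothing passes a Table 13 limit and no tracing need be called abnormal. The Protocol's mean change would show the shift. No SAP table would; a reader would have to compute it from Listing 2.10.1.
2. **A value beyond Table 13 that is not judged significant.** The Protocol would list the subject. Under the SAP the value is printed in Listing 2.10.1, but no stated rule flags it, and the titles of the two tables exclude it.
3. **A value judged clinically significant.** If treatment-emergent, it is counted in Table 3.5.1.1 or 3.5.1.2 and is listed. Nothing is lost here.

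Two comparisons within the SAP suggest an oversight. First, the neighbouring vital-signs section (8.4) keeps by-visit values and change, reproduces the Protocol's Table 12 limits as SAP Table 7, and defines an alert value. The ECG section has no counterpart to any of these, although an alert listing for ECGs remains. Second, the text of 8.5 covers abnormalities at baseline and afterwards, while the table titles cover only treatment-emergent, clinically significant ones, so the section and its own tables do not match.

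**The case against.** The strongest reply is that little is lost. Every ECG value is still to be listed, so anyone can compare it with Table 13, which remains in the Protocol. Appendix A calls its list a guideline, and the table shells sit in a separate document that may define abnormal and alert ECG values. The data are thin: Protocol 7.5.4 schedules ECGs at screening, Week 24 and end of treatment, plus any that are clinically indicated. End of treatment has no fixed time (Protocol 6.4), so mean change there mixes exposure lengths. Enrollment ended early (SAP 10.2.3). The documents also raise no QT concern: the ruxolitinib QT study in Protocol 1.6.1.1 showed no association, and the events of special interest in Protocol 9.4.2.5 include no cardiac term.

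Most of this stands, and it limits the size of the point. It does not remove it. Unseen shells cannot make SAP 10.1 correct. Early termination is given as the reason for SAP Amendment 3 but is not linked to ECGs, and the vital-sign summaries were kept. The QT study cited concerns ruxolitinib; the documents available here report none for INCB050465.

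A reader might infer four stronger things, which the documents do not support:

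- That the SAP leaves nothing but tabulated abnormalities. Listings 2.10.1 to 2.10.3 contradict this.
- That the ECG conclusion would rest on investigator judgement alone. The listed values allow an independent check, and the wording of SAP 8.5 is wider than the table titles.
- That the Protocol promised a count and percentage beyond the Table 13 limits. It promised a listing.
- That alert ECG values must mean Table 13 values. Table 13 defines notable values, and the Protocol defines alert only for vital signs.

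**Conclusion.** The discrepancy is real and minor. SAP 8.5 and Appendix A omit the by-visit summary of all five ECG parameters named in Table 13 and carry none of their limits, and none of the SAP's four change records mentions it. The consequence is confined to two things: a group shift in a parameter would appear in no summary table, and notable values would have no stated criterion in the SAP.

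This rests on the SAP text and its list of outputs; the shells were not available. How many participants have values beyond Table 13, or whether any shift exists, cannot be estimated from the documents. Nothing in them points to an ECG signal, and the finding should not be read as suggesting one.

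**What to change.** In SAP 8.5 and Appendix A:

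1. Add by-visit value and change from baseline for QTcF, PR, QRS, QT and RR, by treatment group, at screening/baseline, Week 24 and end of treatment. State that the screening ECG serves as baseline, since it is the only one Protocol 7.5.4 schedules before dosing.
2. Carry Protocol Table 13 into the SAP as the criterion for the listing of notable values, and state which criterion Listing 2.10.3 uses for alert.
3. Align the wording of 8.5 with the titles of Tables 3.5.1.1 and 3.5.1.2.

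A number and percentage beyond the Table 13 limits by treatment group would be a sensible optional addition, labelled as new and not as a return to the Protocol.

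If the summaries were dropped on purpose, correct SAP 10.1 to record the removal and give the reason.

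The cost is one or two standard tables from values already planned for Listing 2.10.1, with no new data collection, or a short entry in SAP 10.1.

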9. INTERIM ANALYSES

There will be no planned, formal interim analyses for the Part 1 dose escalation portion of the study. The review of accrued clinical data will be conducted by Incyte and provided to study investigators via teleconferences at the end of Part 1 of the study. Based on review of the most current safety data, the sponsor (in consultation with the study investigators and using the dose-escalation/de-escalation rules) will determine if and at what dose additional participants should be treated in the study.

For TG5D and TG5 (TG5I/M) in the safety population, a formal interim analysis for futility is planned after 15 participants are enrolled into each treatment group and have discontinued or had their Week 12 visit. If 4 or fewer participants in a given dose group have spleen stability or a reduction from baseline in spleen volume (ie, percentage change from baseline $\leq 0\%$) as measured by MRI (or CT scan in applicable participants), then the dose in question will be terminated.

If either TG5D or TG5 (TG5I/M) is terminated, then Part 4 will continue as a single-arm study, and the primary endpoint will be analyzed as described in Section 3.6. If both of the treatment groups are terminated, the study will be terminated. The probabilities of stopping a treatment group for futility for various probabilities of a participant achieving $\geq 0\%$ decrease in spleen volume at Week 12 are provided in [Table 8](#). Additional operational details of the interim analyses, including TFLs provided to the DMC, will be provided in the DMC Charter.

Table 8: Probability of Stopping a Treatment Group for Futility

Probability of Participant Having $\geq 0\%$ Decrease in Spleen Volume at Week 12 in a Treatment Group	Probability of Stopping a Treatment Group for Futility
5%	99.5%
10%	94.4%
20%	64.8%
25%	46.1%
30%	29.7%
40%	9.1%
50%	1.8%

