There will be 1 planned interim analysis conducted for futility for this study. The interim analysis will be conducted during the randomized portion of the study once TG5D and TG5I/M + TG5 enroll 15 subjects and have been evaluated for spleen volume at Week 12. Further enrollment in a treatment group will be terminated if fewer than 4 subjects in the treatment group have spleen stability or a reduction from baseline in spleen volume (ie, percentage change from baseline  $\leq 0\%$ ) as measured by MRI (or CT scan in applicable subjects) at Week 12. Subjects remaining in any terminated group may have their dose adjusted to reflect the ongoing group with sponsor approval.

If either TG5D or TG5I/M is terminated, then Part 4 will continue as a single-group study, and the primary endpoint will be analyzed. If both TG5D and TG5I/M are terminated, then the study will be terminated. The probabilities of stopping a treatment group for futility for various probabilities of a subject achieving  $\geq 0\%$  decrease from baseline in spleen volume at Week 12 are provided in the full body of the Protocol.

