### 9.5.2. Interim Efficacy Analysis

There will be 1 planned interim analysis conducted for futility for this study. The interim analysis will be conducted during the randomized portion of the study once TG5D and TG5I/M + TG5 enroll 15 subjects and have been evaluated for spleen volume at Week 12. Further enrollment in a treatment group will be terminated if fewer than 4 subjects in the treatment group have spleen stability or a reduction from baseline in spleen volume (ie, percentage change from baseline  $\leq 0\%$ ) as measured by MRI (or CT scan in applicable subjects) at Week 12. Subjects remaining in any terminated group may have their dose adjusted to reflect the ongoing group with sponsor approval.

If either TG5D or TG5I/M is terminated, then Part 4 will continue as a single-group study, and the primary endpoint will be analyzed as described in Section 9.4.1.4. If both of the treatment groups are terminated, then the study will be terminated. The probabilities of stopping a treatment group for futility for various probabilities of a subject achieving  $\geq 0\%$  decrease in spleen volume at Week 12 are provided in Table 16.

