**Table 16: Probability of Stopping a Treatment Group for Futility**

Probability of Subject Having $\geq 0\%$ Decrease in Spleen Volume at Week 12 in a Treatment Group	Probability of Stopping a Treatment Group for Futility
5%	99.5%
10%	94.4%
20%	64.8%
25%	46.1%
30%	29.7%
40%	9.1%
50%	1.8%

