3.7.2. Sample Size in Randomized Portion

The sample size and power calculations for the randomized portion of the study are based on a 2-sample Wilcoxon rank sum test with a normal approximation applied to the test statistic. The data from Study INCB 18424-351 (COMFORT-1) suggested a mean reduction of 8.44 in percentage change from baseline of spleen volume with a standard deviation of 14.5 from baseline to Week 12 for the active group in that study. For a 2-sided Type I error of 0.10 and Type II error of 0.10 with 30 participants per treatment group, the test is powered to detect an 11.4 percentage point location shift between the 2 groups in regards to percentage change in spleen volume. The 2 populations are assumed to be normally distributed with a common standard deviation of 14.5.

In the event that only 1 dose was selected during the Part 1 safety-run in portion of the study or the event that 1 of the treatment groups was terminated for futility at the interim analysis during the randomized portion, the median spleen volume reduction would be estimated and a CI constructed based on the exact binomial CI. [Figure 4](#) plots the power of the design with 30 participants per treatment group at various percentage point location shifts between the 2 groups in spleen volume reduction.

Figure 4: Plot of Power at Various Differences Between Treatment Groups

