5.2. Treatment Groups

As the study was terminated early, participants from all parts will be combined. Data will be summarized overall and by treatment group based on the dose regimen initially assigned in the initial portion:

- TG10: Ruxolitinib at stable dose plus INCB050465 10 mg QD for 8 weeks followed by 10 mg once weekly.
- TG20: Ruxolitinib at stable dose plus INCB050465 20 mg QD for 8 weeks followed by 20 mg once weekly.
- TG5, TG5I/M: Ruxolitinib at stable dose plus INCB050465 20 mg QD for 8 weeks followed by 5 mg QD.
- TG5D: Ruxolitinib at stable dose plus INCB050465 5 mg QD from Day 1 until EOT visit.

Note that TG5I/M in Part 4 is identical to TG5 from Part 3; participants from these 2 groups will be combined in the final analysis.

The crossover participants will be summarized in the initial portion from the date of randomization to the date before crossover.

In the crossover portion, the crossover participants will be summarized in TG5D from the date of crossover to the end of study. Only the crossover participants will be summarized in the crossover portion. Participants in TG5 (TG5I/M) and TG5D and the participants in TG10 or TG20 who do not meet the crossover criteria will remain in the treatment group initially assigned in the initial portion.

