- Incorporation of administrative changes. Other minor, administrative changes have been incorporated throughout the SAP.

10.2.3. Amendment 2 to Amendment 3

The primary purpose of this amendment is to update the statistical analyses as enrollment has been terminated early.

- Intent-to-treat population, per-protocol population, and safety run-in population were removed. All analyses will be conducted using the safety population.
- In addition to the comparison between TG5D and TG5I/M, the comparison between daily dosing (TG5D + TG5I/M) and daily/weekly dosing (TG10 + TG20) in the endpoints of interest were added.
- The algorithm of the window for deriving MFSAF v3.0 total symptom score for baseline, Week 12, and Week 24 in Table 4 was updated to fix the issue when the participants have missing values in the end of window.
- Elevations in liver chemistry tests were added.
- Incorporation of administrative changes. Other minor, administrative changes have been incorporated throughout the SAP.

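### SAP Section 9 stops a group for futility at 4 or fewer of 15, the Protocol at fewer than 4, and SAP Table 8 gives the probabilities for the Protocol's rule

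*SAP*

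**What the plan says.** Protocol Section 9.5.2 plans one futility analysis once the two groups being compared (TG5D, and TG5I/M combined with TG5) have enrolled 15 subjects and been evaluated for spleen volume at Week 12. The criterion is a percentage change from baseline of 0% or less. Enrollment in a group "will be terminated if fewer than 4 subjects in the treatment group have spleen stability or a reduction from baseline in spleen volume". The synopsis, under Statistical Methods, gives the same boundary: "Further enrollment in a treatment group will be terminated if fewer than 4 subjects in the treatment group have spleen stability or a reduction".

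SAP Section 9 plans the same look, at 15 participants per group and with the same criterion, but words the boundary differently: "If 4 or fewer participants in a given dose group have spleen stability or a reduction from baseline in spleen volume", the dose is terminated.

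Each document then tabulates the probability of stopping a group at seven true rates (Protocol Table 16, SAP Table 8). The two tables agree in every entry. SAP Section 10.1, which is reserved for changes to Protocol-defined analyses, records none, and the version history in SAP Section 10.2 lists no change of boundary.

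**The concern.** With X the number of participants meeting the criterion, fewer than 4 means X ≤ 3, and 4 or fewer means X ≤ 4. Both documents use 15 per group, so the rules disagree at exactly X = 4. If the probabilities in SAP Table 8 belong to one rule and the sentence above them states the other, the SAP contradicts itself as well as the Protocol.

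The boundary carries weight. In both documents, stopping one group turns Part 4 into a single-group study, in which the randomized comparison gives way to an estimated median with a confidence interval. Stopping both groups ends the study.

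**Working it through.** **Inputs**
- n = 15 per group: Protocol Section 9.5.2 and SAP Section 9.
- Boundary X ≤ 3: Protocol Section 9.5.2 and synopsis. Boundary X ≤ 4: SAP Section 9.
- True rates p and printed stopping probabilities: SAP Table 8, identical to Protocol Table 16.
- Planning figures: SAP Section 3.7.2, "a mean reduction of 8.44 in percentage change from baseline of spleen volume with a standard deviation of 14.5", with normality assumed. They come from the active group of another study.

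**Formula.** P(stop) = Σ C(15, k) p^k (1 − p)^(15 − k), summed over k = 0 to c, with c = 3 for the Protocol rule and c = 4 for the SAP wording.

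**One row in full, p = 20%.** The terms for k = 0 to 4 are 3.518, 13.194, 23.090, 25.014 and 18.760%. The first four sum to 64.816%, which is the printed 64.8%. Adding the fifth gives 83.577% (from unrounded terms).

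**All rows**

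| True rate | Printed | P(X ≤ 3) | P(X ≤ 4) | Difference, P(X = 4), in points |
|---|---|---|---|---|
| 5% | 99.5% | 99.45% | 99.94% | 0.5 |
| 10% | 94.4% | 94.44% | 98.73% | 4.3 |
| 20% | 64.8% | 64.82% | 83.58% | 18.8 |
| 25% | 46.1% | 46.13% | 68.65% | 22.5 |
| 30% | 29.7% | 29.69% | 51.55% | 21.9 |
| 40% | 9.1% | 9.05% | 21.73% | 12.7 |
| 50% | 1.8% | 1.76% | 5.92% | 4.2 |

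The X ≤ 3 column reproduces every printed entry (at 40% the unrounded value is 9.0502%, which rounds to 9.1%). The X ≤ 4 column reproduces none. A search over group sizes 5 to 59 with every possible cutoff found that only n = 15 with cutoff 3 reproduces the whole table, so no other group size reconciles it with the SAP's wording. The difference is largest at p = 4/15 = 26.7%, where P(X = 4) = 22.8%.

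**Two groups.** If both had an assumed true rate of 40% and were independent, the chance that at least one stops is 1 − (1 − 0.09050)² = 17.3% under X ≤ 3 and 1 − (1 − 0.21728)² = 38.7% under X ≤ 4.

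**At the planning figures.** The probability of a change of 0% or less is Φ(8.44/14.5) = Φ(0.582) = 0.720. Then P(X ≤ 3) = 0.004% and P(X ≤ 4) = 0.035%.

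**With missing scans.** The SAP counts participants who discontinued among the 15, and neither document says how a missing Week 12 scan enters the futility count. If it counts as not meeting the criterion:
- An assumed 20% missing gives p = 0.8 × 0.7197 = 0.576 and stopping probabilities of 0.35% and 1.6%.
- An assumed 40% missing gives p = 0.6 × 0.7197 = 0.432 and stopping probabilities of 5.7% and 15.1%.

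**The case against.** The contradiction and the arithmetic are not in dispute. The strongest case against the point concerns its consequence.

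*The intended rule is fairly clear.* The synopsis, Protocol Section 9.5.2 and both tables point to fewer than 4. One SAP phrase stands alone, and the absence of any declared change in SAP Section 10.1 suggests a slip of wording rather than a new rule. This stands as to intention. It does not show which boundary was used, or would have been used, by someone following the SAP as written.

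*The practical effect may be nil.* SAP Amendment 3 says of itself: "The primary purpose of this amendment is to update the statistical analyses as enrollment has been terminated early". Section 5.2 confirms it: "As the study was terminated early, participants from all parts will be combined". A rule that ends further enrollment has little left to act on, and no final efficacy analysis uses the boundary. It would matter only if the interim analysis was run and a group had exactly 4 of 15. The documents report neither, and operational details are left to a DMC Charter that is not available here. This limits the effect on conduct, but the final SAP still presents the analysis as planned.

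*The large differences lie at assumed rates.* This is also fair. The documents do not define the rate that makes a regimen worth continuing, and at the SAP's planning figures stopping is rare under either rule. Those figures, however, come from another study's active group, whereas this trial enrolls patients with a suboptimal response on ruxolitinib, so they do not settle the matter.

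*Nothing is miscalculated.* Both tables are correct for the Protocol's rule. The error is a mismatch between text and table.

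**Conclusion.** The concern holds. The futility boundary in the final SAP contradicts the Protocol body, the Protocol synopsis and the SAP's own Table 8, and the difference is not declared. If the SAP wording were followed, the printed stopping probabilities would be too low by 12.7 to 22.5 points at true rates of 20% to 40%, and by 4.3 points or less at 5%, 10% and 50%. These figures rest only on the binomial model with n = 15, which is the model that reproduces the tables. The effect on how the trial was run cannot be determined from the documents. The point should be fixed because the threshold decides whether a group closes, but it does not by itself put the final efficacy analysis in doubt.

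**What to change.** Reconcile the passages in one of two ways.

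1. Change the SAP Section 9 boundary to fewer than 4. It then agrees with Protocol Section 9.5.2, the synopsis and both tables, and nothing else has to change. The cost is one phrase.
2. If 4 or fewer was intended, replace the entries of SAP Table 8 and Protocol Table 16 with 99.9, 98.7, 83.6, 68.6, 51.5, 21.7 and 5.9%, amend Protocol Section 9.5.2 and the synopsis, and declare the change in SAP Section 10.1. The cost is one recomputed table in each document, two Protocol sentences and one SAP entry.

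In either case, if the interim analysis was run, state which boundary was applied. No extra data or participants are needed.
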